### **4.3 Discontinuation of Study Subjects**

Subjects will be encouraged to complete the study through the treatment and post-treatment follow up periods. Each subject is free to discontinue from the study at any time, for any reason, and without penalty or loss of benefit. Participation in the study treatment may be discontinued for any of the following reasons:

- Occurrence of any medical condition or circumstance that exposes the subject to substantial risk and/or does not allow the subject to adhere to the requirements of the protocol, including early removal of LYR-210 (Section 6.5).
- Any serious AE (SAE, Section 8.4.9.2), clinically significant AE, severe laboratory abnormality, intercurrent illness, or other medical condition that indicates to the Investigator that continued participation is not in the best interest of the subject.
- Subject's decision to withdraw.
- Requiring ESS as rescue treatment.
- If deviations to the use of prohibited medications occur after randomization and study treatment, the Investigator in consultation with the Sponsor and Sponsor's medical monitor will decide on a case-by-case basis whether the subject may continue in the study based on the time the prohibited medication was administered and its pharmacology.
- Subject's failure to comply with protocol requirements or study related procedures.
- Termination of the study by the Sponsor or a regulatory authority that has provided approval to proceed.

Subjects who withdraw or are withdrawn from the study treatment will be requested to return to the clinic for the assessments and procedures scheduled for the EOT visit and the safety follow up visits post EOT (Section 8.1).

The Investigator or study staff will document the reason(s) for subject discontinuation on the Case Report form (CRF), notify the IRB/EC as required by their Institution's procedures, and notify the Sponsor the reason for discontinuation.

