#### **6.4.4 Rescue Concomitant Medications and Treatment**

The following rescue medications are recommended in the event of an acute exacerbation of the following conditions that result in the subject contacting the Investigator who determines an initiation of rescue therapy:

- Any time during the 24-week treatment stage:
  - After a clinic visit and per Investigator's judgment, antibiotics for sinus infection.
  - After a clinical visit and evaluation for worsening or uncontrolled severe CS symptoms, the Investigator using his/her best judgement may give a course of oral corticosteroids. Typical indications include persistent sinus infection after an initial course of antibiotics while starting another course of antibiotics, uncontrolled sinus inflammation not responding to an INCS, or a flare-up of asthma. The rationale for the use of oral corticosteroid must be recorded.
- After the Week 4 visit only:
  - For acute allergic symptoms: non-sedating oral antihistamine such as loratadine (10 mg per day) or equivalent.
  - For severe acute nasal blockage (score of 2 or more over the past 3 days): a course of oxymetazoline spray for a maximum of 3 consecutive days and a total maximum of 10 days during the treatment period. Oxymetazoline cannot be used within 24 hours before MRI assessments.
  - For worsening CS symptoms: intranasal MF sprays with dose and duration per Investigator's recommendation.
  - For worsening or uncontrolled severe CS symptoms: ESS as rescue treatment per Investigator's recommendation.

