5.6. PER PROTOCOL ANALYSIS SET [PPAS]

The per-protocol analysis set (PPAS) will contain all randomized subjects who received the study treatment, have post-Day 1 assessments as specified in Section 5.5, and are without major protocol deviations at the time of the primary analysis. A major protocol deviation is defined as any protocol deviation potentially affecting the evaluation of the primary and key secondary efficacy endpoints. It is to be noted that a protocol deviation classified as major by the Biostatistical team (resulting in the exclusion of a subject from the PPAS) might be classified as critical, major or even minor by the Clinical team as the Clinical and Biostatistical teams are using different criteria. Please refer to the Protocol Deviations Management Plan for the criteria used by the Clinical team to classify each protocol deviation as critical, major or minor.

This analysis set will be used to perform supportive analysis for the primary, key secondary, and other secondary efficacy including CS7DA4S, 7-day average score of individual symptoms, SNOT-22, and MRI analyses. Major protocol deviations and other reasons for exclusion from the PP analysis set will be identified and finalized by [REDACTED] Biostatistics based on blinded review of the data, prior to the data extraction for the primary analysis and unblinding of the treatment code.

Major protocol deviations and other reasons for excluding subjects from the PPAS include:

- Insufficient essential efficacy data
 - The primary efficacy variable is the change from baseline (CFBL) in the CS7DA4S score at Week 4. The

CFBL for this score will be derived in the ePRO data at the Week 4 timepoint. The subject must have a non-missing CFBL value for CS7DA4S at Week 4.

- Non-eligibility with the protocol specified inclusion/exclusion criteria
 - The subject must have a composite score of CS7DA4S ≥ 7 at Day 1, as derived by ██████████ Biostatistics. A minimum of five daily entries are required for composite score calculation over the seven days leading up to and including Day 1 for assessing the subject's eligibility for participating in the study.
- Use of prohibited rescue medications prior to Week 4 visit, as identified in a regular Medical Data Review and recorded in the Clinical Trial Management System (CTMS) log for protocol deviations. Such medications include:

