 - Oral antihistamine, excluding perennial allergic rhinitis patients who have been on a stable dose of antihistamine since screening
 - Nasal decongestants
 - Intranasal corticosteroid sprays
- Insufficient exposure to the study treatment
 - The subject must have been exposed to the treatment for at least 16 weeks. Exposure will be derived as described in Section 13.1.
- Actual and planned treatments are not the same
 - This will be identified at study unblinding, at the time of the primary analysis, by comparing the subject's allocated treatment arm to the kit type of the kit administered to the subject. The randomization data provided by the randomization vendor will be used.
- Pregnancy: Pregnant subjects are not allowed to participate in the study. Pregnancy results are recorded on the Urine Pregnancy Test, and Serum Pregnancy Test eCRFs.

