6.6.1. DAILY DIARY VISIT ASSIGNMENT

The daily diary data do not associate assessments with visits. The date of assessment is collected and will be used to assign the ePRO data to specific visits as required for the definition of various endpoints. The CS7DA4S score is the average of the total daily scores for the 4 CS cardinal symptoms over the 7 days leading up to and including a visit (refer to Section 15.1.1).

The selection of the total daily scores to use to derive CS7DA4S and the 7-day average CS score for the 4 symptoms

for a respective visit is displayed in [Table 2: Daily Diary Visit Assignment](#). For example, in order to derive the Week 2 CS7DA4S, the average of the 7 total daily scores for relative days 9 to 15 will be used.

Table 2: Daily Diary Visit Assignment

Assigned Visit	Target Day	CS7DA4S Range	
		Lower Limit	Upper Limit
Baseline ^a	1	-6	1
Week 1 ^b	8	2	8
Week 2 ^b	15	9	15
Week 3 ^b	22	16	22
Week 4 ^b	29	23	29
Week 8 ^b	57	51	57
Week 12 ^b	85	78	85
Week 16 ^b	113	107	113
Week 20 ^b	141	135	141
Week 24	169	163	169
4 weeks post-treatment ^c	28	21	28
8 weeks post-treatment ^c	56	49	56
12 weeks post-treatment ^c	84	77	84
16 weeks post-treatment ^b	112	105	112
20 weeks post-treatment ^c	140	133	140
24 weeks post-treatment ^c	168	161	168

^a See Section 6.3, the planned timepoint for Baseline is Day 1.

^b For Weeks 2 to 24, target day is calculated relative to the reference start date (refer to Section 6.1)

^c For post-treatment visits, target day is calculated relative to end of treatment date (refer to Section 6.2).

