13.1. DERIVATIONS

Duration of exposure is calculated as below and will be rounded to 1 decimal place:

$$\text{Duration of exposure (weeks)} = \frac{\text{date of event} - \text{date of insertion procedure} + 1}{7}$$

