15.1.4. SENSITIVITY ANALYSIS OF PRIMARY EFFICACY ENDPOINT

The following sensitivity analyses to the primary analysis of the primary endpoint will be performed:

Sensitivity to the analysis set

The primary analysis of the primary efficacy endpoint will be repeated for the PPAS.

Sensitivity analyses to missing data

- LOCF single imputation method:
 - The CS7DA4S will be calculated as described in Section 15.1.1 for baseline, Week 1, Week 2, Week 3

and Week 4

- If Week 4 CS7DA4S score is missing, then the last available post baseline CS7DA4S prior to Week 4 will be carried forward and will be used as the Week 4 CS7DA4S score and the same analysis as for the primary analysis of the primary efficacy endpoint will be repeated (refer to Section 15.1.3).
- Multiple imputation will be implemented using 3 steps:
 - First, intermittent missing CS7DA4S data will be imputed under the missing at random (MAR) assumption using a multivariate joint Gaussian imputation model and the Monte Carlo Markov Chain (MCMC) method. A separate imputation model will be estimated for each treatment group separately. The imputation models will include the baseline CS7DA4S values as a covariate and the stratification variables and weekly CS7DA4S (Weeks 1 to 4) as factors. The MAR mechanism assumed that subjects have unobserved values in line with similar subjects with available data in their treatment group, taking into account their values observed prior to the weeks with missing data. The MAR assumption is reasonable for the Sham patients as it accounts for the trial effect while no active treatment is taken. It is also a reasonable assumption for the LYR-210 subjects as subjects will remain on randomized treatment while intermittent missing data may occur and thus, may be modeled based on similar subjects from their randomized treatment group. The MCMC method will be used with a random seed number of 2575, multiple chains, a burn-in of 200 iterations, and non-informative prior. During this step, 50 imputed datasets will be created.

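### The single per-protocol set's 16-week exposure minimum drops subjects from the Week 4 analysis for events that happen after the Week 4 score has closed

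*SAP*

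**What the plan says.** SAP 5.6 sets up a single PPAS for supportive analyses of the primary, key secondary and several other secondary endpoints. There is no version specific to a visit. Two of its conditions matter here. The subject must have a change from baseline in CS7DA4S at Week 4, and, separately, "The subject must have been exposed to the treatment for at least 16 weeks".

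SAP 13 ends exposure at the recorded end of treatment or at loss of both depots, whichever comes first. Loss of one depot is not an ending; if both are lost at different times, the second date counts. SAP 13.1 adds: "Duration of exposure is calculated as below and will be rounded to 1 decimal place".

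The set is used at visits well before Week 16. For the primary endpoint, SAP 15.1.4 says: "The primary analysis of the primary efficacy endpoint will be repeated for the PPAS". SAP 15.2.4.1 uses the same set for CS7DA4S and for the four individual symptoms, which are scored from Week 1. SAP 15.2.4.5 uses it for SNOT-22, scored from Week 2. Diary scores are averages "over the 7 days leading up to and including a visit" (SAP 6.6.1), and SAP Table 2 fixes the Week 4 score to Days 23 to 29.

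Protocol 10.1 states no exposure minimum. Its data condition is tied to the assessment being analysed. It judges major deviations once, at the primary analysis, and leaves the final definition of the set to blinded review.

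**The concern.** A per-protocol repeat of the Week 4 analysis should show whether the result holds among subjects who followed the plan up to Week 4. Under the 16-week rule, membership also depends on what happens over roughly the following twelve weeks. A subject can have a complete Week 4 score, still count as exposed when it closes, and yet be removed because exposure ended later.

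These later events are not clearly unrelated to arm or outcome. Loss of both depots can happen only with LYR-210. Early end of treatment can happen in any arm; Protocol 4.3 lists "Requiring ESS as rescue treatment" among the reasons for it. Protocol 6.4.4 places that rescue under "After the Week 4 visit only" and describes it as "For worsening or uncontrolled severe CS symptoms: ESS as rescue treatment", so it falls inside the period at issue. A difference between the ITT and PPAS results at Week 4 could then reflect Weeks 5 to 16 rather than adherence up to Week 4.

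**Working it through.** **Planning figure.** The plan gives no figure for the effect of this rule. The illustration below borrows the planning inputs in SAP 7.1: means of -3.00 and -1.30 (difference -1.70), SD 2.4, 21 evaluable per arm, one-sided 0.05. A noncentral t calculation for one dose against sham (40 df) gives 73.0% power, matching the stated 73%.

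**Step 1: the cut-off in days.** SAP 13.1: exposure in weeks = (event date - insertion date + 1)/7, to one decimal. An ending on Day 111 gives 111/7 = 15.9, excluded. Day 112 gives 112/7 = 16.0, included.

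**Step 2: how long after each score closes a subject can still be excluded.** Closing days are from SAP Table 2; the span is 111 minus the closing day.

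| Diary score | Closes | Later endings that exclude | Days |
|---|---|---|---|
| Week 1 | Day 8 | Days 9-111 | 103 |
| Week 2 | Day 15 | Days 16-111 | 96 |
| Week 3 | Day 22 | Days 23-111 | 89 |
| Week 4 (primary) | Day 29 | Days 30-111 | 82 |
| Week 8 | Day 57 | Days 58-111 | 54 |
| Week 12 | Day 85 | Days 86-111 | 26 |

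These spans show opportunity for exclusion, not how often it happens.

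**Step 3: a second condition of the same kind.** The PPAS also requires a Week 4 score. A subject scored at Weeks 1 to 3 but not at Week 4 is dropped from those earlier per-protocol analyses because of data missing later. Protocol 10.1 asks only for data on the assessment being analysed.

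**Step 4: what exclusions could do to the estimate.** The numbers excluded and their scores are assumptions; the documents supply neither. With x of 21 excluded in an arm, and d = mean of the excluded minus the arm mean (a = LYR-210, s = sham):

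PPAS difference = -1.70 - xa·da/(21 - xa) + xs·ds/(21 - xs)

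| Assumption (exclusions in one arm only) | 2 excluded | 4 excluded |
|---|---|---|
| LYR-210 subjects with a sham-like change (da = +1.7) | -1.88 | -2.10 |
| LYR-210 subjects 1.7 better than their arm mean (da = -1.7) | -1.52 | -1.30 |
| Sham subjects with no change (ds = +1.3) | -1.56 | -1.39 |
| Exclusion unrelated to score (d = 0) | -1.70 | -1.70 |

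Equal numbers with equal score deviations in both arms also leave -1.70. For scale, the SE of a pairwise difference is 2.4·√(1/n1 + 1/n2): 0.741 for 21 v 21, 0.760 for 19 v 21 and 0.783 for 17 v 21. The largest shift shown, 0.40, is about half an SE (0.40/0.783 = 0.51).

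**The case against.** The strongest reply is that little depends on this. ITT is the primary efficacy set, the PPAS is supportive, SAP 7.8 reports nominal p-values in a study it calls exploratory, and SAP 9 will list and summarise exclusion reasons by arm. All of that stands and limits the weight of the point. Listing the exclusions, however, does not supply the Week 4 per-protocol estimate with those subjects kept in.

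A second reply is that one fixed set keeps the same subjects across visits, that SAP 5.6 defines major deviations by their effect on both the primary and key secondary endpoints, and that a long minimum makes sense for Week 24. This is fair as a reason for having the minimum. It does not explain applying it to a score that closed on Day 29.

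Four stronger readings are tempting, and the documents do not support them:

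- **The SAP contradicts the protocol.** Protocol 10.1 leaves the definition of the set to blinded review, so an exposure minimum is within what it delegates.
- **The excluded subjects were fully treated.** Loss of one depot does not end exposure under SAP 13. Someone who lost one depot early and the other after Day 29 had only one in place for part of the Week 4 period. The accurate statement is that they still counted as exposed.
- **The rescue criterion shows the list to be inconsistent.** That criterion, "Use of prohibited rescue medications prior to Week 4 visit", stops at Week 4 because Protocol 6.4.4 recommends those types of medication as rescue only after that visit. The cut-off follows the protocol.
- **The rule favours LYR-210.** The illustration moves in both directions, and no rate of both-depot loss or early end of treatment is given.

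**Conclusion.** The point holds for the per-protocol analyses only. As written, the Week 4 PPAS repeat conditions on events up to 82 days after the primary score closes, and those events can differ by arm or by outcome. The same applies to the other endpoints before Week 16. The cut-off and the spans follow directly from SAP 5.6, 13.1 and Table 2 and need no assumption. The size and direction of any bias cannot be derived from the documents and may be zero; the shifts shown rest on assumed counts and scores. Nothing here affects the primary ITT analysis. The correction is worth making because the PPAS repeat is the one planned check of the Week 4 result against the choice of analysis set, and a cleaner version can be derived from dates already collected.

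**What to change.** For the PPAS repeat of the Week 4 primary analysis, require exposure, as SAP 13 defines it, only through Day 29, and say explicitly that loss of one depot does not end exposure. State the rule in days rather than rounded weeks: 28/7 = 4.0, so a rule of 4.0 weeks would admit a subject whose exposure ended on Day 28, before the score closes.

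Keep the 16-week minimum for endpoints at Week 16 and later, including Week 24, and describe it as a tolerance. It accepts up to 169 - 112 = 57 days off treatment before the Week 24 score closes.

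If per-protocol results are reported at other visits before Week 16, apply the same visit-matched rule: Days 8, 15, 22, 57 and 85 for diary scores at Weeks 1, 2, 3, 8 and 12, and the date of the questionnaire used for SNOT-22. At those visits, require data for the assessment being analysed, as Protocol 10.1 does, in place of a Week 4 score.

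The cost is SAP wording and one extra per-protocol flag, or several if other early visits are reported. Denominators will differ by visit, and there will no longer be one fixed set of subjects throughout. No new data are needed.

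The eligibility score window also differs between Protocol 8.3.1.1 (the 7 days before Day 1) and SAP 5.6 (Day 1 included). That is unrelated to the exposure rule and should be reconciled as a separate item.

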5.7. PHARMACOKINETIC ANALYSIS SET [PK]

The PK analysis set (PKAS) will contain all subjects in the SAF set who received LYR-210 and have at least one evaluable plasma drug concentration data point post-Day 1 available. As concentration data are required to assign the PK analysis set, this can only be done at study unblinding, at the time of the primary analysis. Subjects will be analyzed according to the actual treatment successfully received.

Subjects who have used any Mometasone Furoate drugs within one day prior to a PK blood draw would be

identified by “MOMETASONE” in the Base Name of concomitant medications. These PK blood draw timepoints will be excluded from analysis. Similarly, results from PK blood draw timepoints after subjects reported any depot dislodgement will also not be analyzed.

5.8. ASSIGNMENT OF ACTUAL TREATMENT

If a subject receives a study treatment or treatment attempt that is different from their randomized treatment, then the assignment of the actual treatment will be as per the bilateral treatment received or attempted.

6. GENERAL CONSIDERATIONS

6.1. REFERENCE START DATE AND STUDY DAY

Study Day will be calculated from the reference start date and will be used to show start/stop day of assessments and events.

Reference start date is defined as the day of LYR-210 administration/Sham procedure or treatment attempt. Study Day will appear in every listing where an assessment date or event date appears.

- If the date of the event is on or after the reference start date, then:

$$\text{Study Day} = \text{date of event} - \text{reference start date} + 1$$

- If the date of the event is prior to the reference start date, then:

$$\text{Study Day} = \text{date of event} - \text{reference start date}$$

In the situation where the event date is partial or missing, the event date will appear partial or missing in the listings and any corresponding Study Day and durations will appear missing in the listings.

6.2. POST-TREATMENT DAY

The Post-Treatment Day will be calculated for data collected after the Week 24/EOT visit as follows:

$$\text{Post Treatment Day} = \text{date of event} - \text{date of Week 24/EOT visit}$$

6.3. BASELINE

Unless otherwise specified, baseline is defined as the last non-missing measurement taken prior to LYR-210 administration/Sham procedure or treatment attempt (including screening and unscheduled assessments). In the case where the last non-missing measurement and the reference start date coincide (and time is not collected), that measurement will be considered baseline, but AE and medications commencing on the reference start date will be considered post-baseline.

The baseline CS7DA4S score is the average of the 7 days leading up to and including Day 1, that is Day -6 to Day 1 (refer to Section 15.1.1 for further details on the calculation of the CS7DA4S scores).

6.4. UNSCHEDULED VISITS, RETESTS AND EARLY TERMINATION DATA

In general, for by-visit summaries, data recorded at the nominal visit will be presented. Unscheduled measurements will not be included in by-visit summaries if a nominal visit is performed in the same visit window but will contribute to the Last Observation Carried Forward (LOCF) value, and the worst-case value where required (e.g. overall post-baseline abnormal summaries).

In the case of a retest (same visit number assigned), the latest available measurement for that visit will be used for by-visit summaries.

Listings will include scheduled, unscheduled, retest and early termination data.

6.5. DERIVED TIMEPOINT

An EOT timepoint will be derived and presented in the by-visit summaries. Data collected at the Week 24 visit or EOT visit will be pooled together under this EOT timepoint. This derived timepoint is for information purpose only and will not be included in any statistical models. That is, only descriptive statistics will be presented for this timepoint.

6.6. WINDOWING CONVENTIONS

All assessments (scheduled, unscheduled, and early termination visits), excluding daily diary data (refer to Section 6.6.1), will be windowed as per [Table 1: Scheduled Visit Windows](#) to ensure all assessments fall into a scheduled visit in order to ensure all data are presented.

If more than one assessment is mapped to the same analysis visit, the following rules for selection of the assessment to use in the analysis will be applied:

- If a nominal and an unscheduled/early termination assessment are mapped to the same analysis visit, the nominal assessment will be selected over the unscheduled/early termination assessment. However, if the nominal assessment result is missing and the unscheduled or early termination assessment result is non-missing, the unscheduled/early termination assessment will be selected.
- In all other scenarios the visit closest to the target day will be selected. If two assessments were performed equally close to an analysis visit’s target day, one prior to and one after, the assessment before the analysis visit’s target day will be assigned to that analysis visit (except for the follow-up MRI assessment which is scheduled to be performed within 7 days after the Week 24/EOT visit).

Table 1: Scheduled Visit Windows

Assigned Visit	Target Day	Visit Windowing	
		Lower Limit	Upper Limit
Screening		-28	-1
Baseline ^a	1	-28	1
Week 2 ^b	15	2	22
Week 4 ^b	29	23	43
Week 8 ^b	57	44	71
Week 12 ^b	85	72	99
Week 16 ^b	113	100	127
Week 20 ^b	141	128	155
Week 24 ^b	169	156	183
4 weeks post-treatment ^c	28	14	42
8 weeks post-treatment ^c	56	43	70
12 weeks post-treatment ^c	84	71	98
16 weeks post-treatment ^c	112	99	126
20 weeks post-treatment ^c	140	127	154
24 weeks post-treatment ^c	168	155	182

^a See Section 6.3, the planned timepoint for Baseline is Day 1.

^b For Weeks 2 to 24, target day is calculated relative to the reference start date (refer to Section 6.1).

^c For post-treatment visits, target day is calculated relative to end of treatment date (refer to Section 6.2).

